This study aims to capture early user feedback from bimodal MED-EL cochlear implant (CI) recipients using a novel audio streaming paradigm that allows direct, simultaneous streaming from an iOS or Android device to both their CI audio processor and hearing aid. Streaming audio has become ubiquitous and for many patients it is an important part of daily listening habits. Individuals with hearing loss may rely more heavily on Bluetooth streaming to their hearing devices as background noise disparately affects their ability to understand speech. Until now, direct, simultaneous Bluetooth streaming to a MED-EL cochlear implant audio processor and a hearing aid was possible only for Android users, with iOS users requiring a third-party intermediary device in order to receive sounds to both devices. MED-EL Elektromedizinische Geräte GmbH (Austria) recently partnered with Starkey Laboratories, Inc. to develop a bimodal solution that streamlines Bluetooth pairing and allows audio streaming from an iOS device to both ears for patients using a compatible MED-EL audio processor and Starkey hearing aid. MED-EL CI recipients will be able to configure their audio processor for direct streaming with a compatible Starkey hearing aid in the AudioKey application. Once configured in the application, recipients can stream phone calls and media directly from the iOS device to their CI audio processor and hearing aid for a binaural listening experience. This innovation brings Bluetooth streaming access to bimodal MED-EL recipients using iOS or Android devices which may provide improvements to these users' overall satisfaction with their hearing devices and may ultimately reduce their need for technical support from their audiologist. This study aims to capture feedback from early adopters of this new bimodal streaming paradigm between MED-EL and Starkey devices, and to measure ease of use and overall satisfaction with this technology.

2. Aims and Objectives

- 2.1. **Specific Aim 1:** To evaluate subjective user satisfaction with and improvement in aspects of hearing with bimodal streaming when compared to their previous streaming setup.
- 2.2. **Specific Aim 2:** To compare changes in participant streaming behavior and satisfaction with bimodal streaming from Baseline to 1-Week.

3. Study Sites and Investigators

- 3.1. Up to three (3) sites will participate. Sites will complete study procedures in accordance with the protocol including subject consent, device fitting as applicable survey distribution, and data entry.
- 3.2. Each site will obtain Investigational Review Board (IRB) approval and/or acknowledgment of exempt status prior to beginning subject enrollment. The Primary Investigator and Co-Investigator(s) for each site will sign Investigator Agreements and will be expected to collect and submit data in accordance with the requirements of this protocol.

4. Device Description(s)

- 4.1. **AudioKey application:** The MED-EL AudioKey application is a software product which can be used with compatible non-implantable MED-EL products. It is intended to be used on a smartphone with internet connection to remotely control compatible MED-EL audio processors and to provide status information of compatible non-implantable MED-EL products. The AudioKey application is intended to be used by individuals who received at least one of the compatible MED-EL audio processors and caregivers of these individuals. The AudioKey application allows users to customize personal settings, locate lost or misplaced audio processors using the Find My Processor functionality, review device usage statistics of the connected audio processors, and quickly access user manuals. AudioKey can configure devices for Bluetooth streaming including MED-EL audio processors, streaming devices (AudioStream, AudioLink), and compatible Starkey hearing aids. AudioKey is available for free download in Google Play and Apple application stores.

5. Potential Benefits

- 5.1. Bimodal streaming of audio to both ears may provide the following benefits to the listener:
 - 5.1.1. Improvement in clarity and sound quality of music, calls, and other audio streamed from the cellphone
 - 5.1.2. Increased enjoyment of music when streamed from the cellphone
 - 5.1.3. Reduced listening effort when streaming phone calls from the cellphone

5.1.4. Improvement in overall satisfaction with streaming audio from the cellphone

5.1.5. Improvement in overall satisfaction with hearing devices

6. Potential Risks

- 6.1. The AudioKey application does not perform as expected
- 6.2. The audio processor does not receive changes initiated by the AudioKey application
- 6.3. Loud sound sensations are perceived by the listener during audio streaming

7. Study Population and Sample Size

- 7.1. **Study Population:** Adults who have already been implanted with a MED-EL cochlear implant and who are utilizing a Starkey hearing aid that is compatible with the AudioKey application will be recruited for participation.
- 7.2. **Sample Size:** This study will enroll 10 to 20 subjects with a goal of enrolling at least 10 subjects for analysis of the primary endpoint.

8. Duration of the Investigation

- 8.1. Subject recruitment is expected to take place over a period of 6 months. Data will be collected on each subject for a period of up to 3 weeks.
- 8.2. Data management and analysis is expected to be completed over the course of 3 months following final subject completion. The total expected duration of the investigation is 10 months.

9. Study Design

9.1. Prospective, multicenter study.

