9.2. Test Materials and Administration

9.2.1. **Baseline User Survey:** The baseline user survey is intended to be completed by the subject at the baseline interval. Survey questions ask for the subject's experience with Bluetooth streaming and their satisfaction ratings of their

current hearing abilities, hearing devices, and Bluetooth streaming set-up. Subjects who participated in the pairing process of AudioKey application are asked for their rating on ease of use.

9.2.2. **1-Week User Survey:** The 1-week user survey is intended to be completed by the subject after they have completed a trial with AudioKey application. Survey questions ask for the subject's success with maintaining a Bluetooth connection to AudioKey application and their subjective ratings on improvement in clarity, sound quality, enjoyment and ease of listening to different inputs when streaming with AudioKey, as well as improvement in their global satisfaction with their current hearing devices with added use of AudioKey, and likelihood of continued use of AudioKey application.

10. Test Intervals and Procedures

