- 11.3.3. The principal investigator may terminate subject participation from the study due to noncompliance with the study protocol or health concerns that prevent required participation.

- 11.3.4. Withdrawn subjects will continue to be seen by their clinical audiologist but no additional data will be collected.

12. Database and Statistical Analysis

- 12.1. MED-EL North American Clinical Research Department, the study sponsor, will complete data entry, database management, and statistical analysis.

13. Statistics and analysis plan

- 13.1. Descriptive statistics will be used to report baseline characteristics (e.g., age, duration of CI use). Quantitative data will be presented as the mean and standard deviation (SD) or median and range (minimum and maximum).
- 13.2. **Specific Aim 1:** To evaluate subjective user satisfaction with and improvement in aspects of hearing with bimodal streaming when compared to their previous streaming set-up.
 - 13.2.1. Subject responses on the 1-week survey will be reported using descriptive statistics including the percentage response rates for each question/domain.
- 13.3. **Specific Aim 2:** To compare changes in subject streaming behavior and satisfaction with bimodal streaming from baseline to 1-week.
 - 13.3.1. The change in subject response from the baseline to 1-week survey will be summarized using descriptive statistics for the following questions/domains:
 - 13.3.1.1. Frequency of Bluetooth streaming
 - 13.3.1.2. Satisfaction with bimodal streaming

14. Monitoring

- 14.1. Database entry and associated source data (paper surveys and case report forms) will be monitored periodically by the Sponsor.

15. Data Management

- 15.1. Copies of completed case report forms (CRFs) and surveys will be submitted to the Sponsor through secure email. Surveys completed electronically will be captured and stored in a secure electronic survey application. Personal identifiable information is excluded from CRFs and surveys to ensure protection of subject's personal information. The sponsor will use an unambiguous subject identification code to allow identification of all the data reported for each subject, to ensure confidentiality. Data will be extracted from case report forms and surveys and manually entered into a controlled network database.

16. Investigator Agreement

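### Two of the three listed risks, loud sound sensations and changes not reaching the processor, have no described item or event collection, so their frequency cannot be reported from the plan as described

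*Combined protocol and SAP*

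**What the plan says.** Section 6 names three risks:

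- 6.1: "The AudioKey application does not perform as expected"
- 6.2, in summary: a change made in the app fails to reach the processor
- 6.3: "Loud sound sensations are perceived by the listener during audio streaming"

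On the baseline survey, Section 9.2.1 states: "Survey questions ask for the subject's experience with Bluetooth streaming and their satisfaction ratings of their" hearing, devices and streaming arrangement. It adds: "Subjects who participated in the pairing process of AudioKey application are asked for their rating on ease of use".

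On the 1-Week survey, Section 9.2.2 states: "Survey questions ask for the subject's success with maintaining a Bluetooth connection to AudioKey application". The same sentence adds "subjective ratings on improvement in clarity, sound quality, enjoyment and ease of listening to different inputs when streaming with AudioKey", then improvement in global device satisfaction and how likely the subject is to keep using the app.

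Section 13.2.1 reports percentages for every 1-Week question. Section 13.3.1 summarises change from baseline in streaming frequency and in satisfaction with bimodal streaming. Section 11.3.2 requires sites to report withdrawals, terminations and losses to follow-up to the sponsor. Section 11.3.4 states: "Withdrawn subjects will continue to be seen by their clinical audiologist but no additional data will be collected". Sections 14.1 and 15.1 mention case report forms but do not describe their content.

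**The concern.** The study is meant to gather feedback from early users of a new streaming arrangement, and Section 18.2 requires that they be told its known risks. Read together, Sections 9.2.2 and 13.3.1 give each of the five benefits in Section 5 a described counterpart in the data. Two of the three risks have none.

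If the forms match their description, an episode of loud sound, or a setting change that never reached the processor, becomes known only if a subject volunteers it. The sponsor could not then say how often either event occurred, and a report silent on them could not be told apart from a study in which they did not happen. Of the two, 6.3 bears on the subject's safety and comfort; 6.2 is a functional failure.

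**Working it through.** The plan states no figure on this point, and the sample size of 10 to 20 has no stated derivation, so there is nothing to reproduce. The check sets each risk against each described source of data.

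| Source | 6.1 app performance | 6.2 changes not received | 6.3 loud sound |
|---|---|---|---|
| Baseline survey (9.2.1) | Partly: ease-of-use rating, if the subject took part in pairing | None described | None described |
| 1-Week survey (9.2.2) | Partly: keeping the connection | None described | None described |
| Visit procedures (10.1, 10.2) | Device check before study procedures only | None described | None described |
| Reports to sponsor (11.3.2) | None described | None described | None described |
| Analysis (13) | The connection item, through 13.2.1 | None described | None described |
| Case report forms (14.1, 15.1) | Content not shown | Content not shown | Content not shown |

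So one risk is partly covered and two are not covered by anything described. A lost connection is only one way in which an app can fail, hence "partly" for 6.1. The sections present run from 2 to 20 without a break in numbering, and none is an adverse-event or device-deficiency section. Section 16.1 cites 21 CFR Part 812, but only for documents due before a site starts.

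**Is 9.2.2 a full list of items?** No. Section 13.3.1 needs 1-Week answers on streaming frequency and on satisfaction with bimodal streaming, and 9.2.2 names neither. Absence from 9.2.2 is therefore not proof of absence from the form.

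**How likely is it that there is something to record?** Input: n = 10 or 20 (Section 7.2). The documents give no event rate, so p is an assumption, shown over a range. With independent subjects, P(at least one affected) = 1 − (1 − p)^n.

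| Assumed p | n = 10 | n = 20 |
|---|---|---|
| 5% | 1 − 0.95^10 = 40% | 1 − 0.95^20 = 64% |
| 10% | 1 − 0.90^10 = 65% | 1 − 0.90^20 = 88% |
| 20% | 1 − 0.80^10 = 89% | 1 − 0.80^20 = 99% |

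**What could an added item show?** With zero events, the exact two-sided 95% upper limit is 1 − 0.025^(1/n):

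- n = 10: 1 − 0.025^(1/10) = 30.8%
- n = 20: 1 − 0.025^(1/20) = 16.8%

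Here n is the number who answer the item. If fewer answer than enrol, the limits are wider.

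**The case against.** **The forms are not shown.** The surveys and case report forms may already hold the missing items, and 9.2.2 is demonstrably incomplete. This stands. The point is limited to the plan as described, and it cannot be said that no field exists. If the items exist, what remains is to name them in 9.2.2 and report them in Section 13.

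**Not all three risks are missed.** A reader might infer that none of the risks in Section 6 is collected. The documents do not support that: the connection and pairing items bear on 6.1.

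**The plan does not report benefits only.** A reader might infer this from the ratings worded as improvement. It is not so. Connection success, intention to continue, and change in streaming frequency and satisfaction can all come out unfavourably, and 13.2.1 reports every 1-Week question. None of these, however, identifies loud sound or a failed change as the cause.

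**Stopping streaming is not withdrawal.** A subject who stops streaming because of loud sound can stay in the study, complete the 1-Week survey and rate continued use low. Section 11.3.4 applies only to those who withdraw. This stands: the loss of data is confined to withdrawn subjects. Section 18.4 keeps what they gave earlier, but before the 1-Week survey that means baseline answers.

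**No aim concerns safety, and the sample is small.** Both aims concern satisfaction and streaming behaviour, the plan makes no claim of zero events, and 10 to 20 subjects estimate a rate poorly. All of this stands and limits the weight of the point. It does not remove the reason to count events that the protocol itself lists as risks.

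**Conclusion.** The concern holds in a limited form. Of the three risks in Section 6, 6.1 is partly covered; 6.2 and 6.3 have no described survey item, and no event collection or analysis is described that would fill the gap. As described, the plan cannot give the frequency of either.

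The conclusion rests on the protocol's account of its surveys, not on the forms, so confidence is medium. The chance that at least one subject is affected by a given risk runs from 40% (5% rate, n = 10) to 99% (20% rate, n = 20). These rates are assumptions and not estimates from the documents. Neither stated aim is undermined. This is a cheap improvement to what is collected, not a flaw in the main analysis.

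**What to change.** 1. **1-Week survey (9.2.2).** Add short items, each asking whether the event occurred and how often: one for 6.2, one for 6.3, and one for app problems other than a lost connection (6.1). Subjects who stopped streaming but remain in the study should answer them too. If such items already exist, name them in 9.2.2.
2. **Withdrawing subjects (11.3.4).** Ask the same items once at the time of withdrawal, with the subject's agreement, and amend 11.3.4 to allow it; as written, that section rules out further data.
3. **Subjects lost to follow-up (11.3.2).** Ask the items at the contact attempt already required there. That duty covers only subjects lost to follow-up, so it cannot serve for withdrawals.
4. **Analysis (13).** Report n/N with an exact 95% CI for each listed risk, where N is the number who answered. State that zero events would still leave a two-sided upper limit of about 31% with 10 subjects or 17% with 20.

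The cost is three short questions, one table line per risk and a small edit to 11.3.4. Survey burden rises slightly. Sample size, visits and the two aims do not change.

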9.2. Test Materials and Administration

9.2.1. **Baseline User Survey:** The baseline user survey is intended to be completed by the subject at the baseline interval. Survey questions ask for the subject's experience with Bluetooth streaming and their satisfaction ratings of their

current hearing abilities, hearing devices, and Bluetooth streaming set-up. Subjects who participated in the pairing process of AudioKey application are asked for their rating on ease of use.

9.2.2. **1-Week User Survey:** The 1-week user survey is intended to be completed by the subject after they have completed a trial with AudioKey application. Survey questions ask for the subject's success with maintaining a Bluetooth connection to AudioKey application and their subjective ratings on improvement in clarity, sound quality, enjoyment and ease of listening to different inputs when streaming with AudioKey, as well as improvement in their global satisfaction with their current hearing devices with added use of AudioKey, and likelihood of continued use of AudioKey application.

10. Test Intervals and Procedures

10.1. Baseline Visit (completed after subject is consented)

10.1.1. The subject's hearing aid and audio processor are verified by the study site to be functioning appropriately prior to study procedures.

10.1.2. The AudioKey application is installed on the subject's cellphone if not already downloaded. The subject's audio processor and hearing aid are paired to AudioKey application. Subject is then trained on application use for bimodal streaming during the 1-week trial.

10.1.3. The Baseline User Survey is completed by the subject.

10.2. 1-Week Visit (1-3 weeks after Baseline)

10.2.1. Subjects complete the 1-Week User Survey. Subjects who have agreed to receive surveys electronically receive a link to complete the survey via email. Subjects who have not agreed to complete the survey electronically are provided a paper copy of the survey and are asked to return it to their investigative site promptly after completion.

10.2.2. Subject participation in the study is complete once the 1-Week User Survey is received.

11. Subject Selection and Withdrawal

11.1. Inclusion Criteria:

- 11.1.1. Implanted with a MED-EL cochlear implant in one ear
- 11.1.2. Consistently using a MED-EL audio processor that is compatible with AudioKey (SONNET (EAS), SONNNET 2 (EAS), SONNET 3 (EAS), RONDO 3)
- 11.1.3. Has access to a MED-EL streaming device if needed (SONNET (EAS)/SONNET2 (EAS)/RONDO 3 users)
- 11.1.4. Using a Starkey hearing aid in the nonimplanted ear that is compatible with the AudioKey application
- 11.1.5. Using a smartphone that can support the AudioKey application
- 11.1.6. Able to complete a survey via cellphone or computer
- 11.1.7. Prior experience with Bluetooth streaming OR expressed motivation to Bluetooth stream to hearing devices
- 11.1.8. Ability to complete all study procedures including provide responses to survey questions

11.2. Exclusion Criteria:

- 11.2.1. Unable to provide reliable feedback
- 11.2.2. Unable to operate a smartphone with or without assistance

11.3. Subject Withdrawal:

- 11.3.1. Subjects may choose to withdraw themselves from the study at any point during participation without fear of repercussion.
- 11.3.2. Investigators should report subject withdrawals, terminations, and subjects who are lost-to-follow up to the Sponsor immediately. Every effort should be made to contact subjects lost-to-follow-up and determine reason for noncompliance.
- 11.3.3. The principal investigator may terminate subject participation from the study due to noncompliance with the study protocol or health concerns that prevent required participation.

- 11.3.4. Withdrawn subjects will continue to be seen by their clinical audiologist but no additional data will be collected.

12. Database and Statistical Analysis

- 12.1. MED-EL North American Clinical Research Department, the study sponsor, will complete data entry, database management, and statistical analysis.

13. Statistics and analysis plan

- 13.1. Descriptive statistics will be used to report baseline characteristics (e.g., age, duration of CI use). Quantitative data will be presented as the mean and standard deviation (SD) or median and range (minimum and maximum).
- 13.2. **Specific Aim 1:** To evaluate subjective user satisfaction with and improvement in aspects of hearing with bimodal streaming when compared to their previous streaming set-up.
 - 13.2.1. Subject responses on the 1-week survey will be reported using descriptive statistics including the percentage response rates for each question/domain.
- 13.3. **Specific Aim 2:** To compare changes in subject streaming behavior and satisfaction with bimodal streaming from baseline to 1-week.
 - 13.3.1. The change in subject response from the baseline to 1-week survey will be summarized using descriptive statistics for the following questions/domains:
 - 13.3.1.1. Frequency of Bluetooth streaming
 - 13.3.1.2. Satisfaction with bimodal streaming

14. Monitoring

- 14.1. Database entry and associated source data (paper surveys and case report forms) will be monitored periodically by the Sponsor.

15. Data Management

- 15.1. Copies of completed case report forms (CRFs) and surveys will be submitted to the Sponsor through secure email. Surveys completed electronically will be captured and stored in a secure electronic survey application. Personal identifiable information is excluded from CRFs and surveys to ensure protection of subject's personal information. The sponsor will use an unambiguous subject identification code to allow identification of all the data reported for each subject, to ensure confidentiality. Data will be extracted from case report forms and surveys and manually entered into a controlled network database.

16. Investigator Agreement

- 16.1. Prior to commencement of the Clinical Investigation at each Site, the investigators shall have signed the Investigator Agreement, obtained IRB approval or exemption for this Investigational Plan and any associated consent materials to be used, and submitted the documentation required by 21 CFR Part 812 to the Sponsor.

17. Investigational Review Board (IRB)

- 17.1. The protocol and associated materials will be reviewed by a centralized IRB to ensure protection of human subjects during the retrospective review of medical records. In addition, the IRB at each investigational site will review the investigational plan and any consent materials, if required, prior to study start. Sites will provide a copy of IRB approval or institutional IRB acknowledgement of centralized IRB approval to the study sponsor prior to data upload.

18. Informed Consent

- 18.1. The consent form included with the protocol will be provided to each investigative site.

- 18.2. Written documentation of Subject's consent must be obtained prior to initiating data collection. The Subject must be verbally informed as to the purpose of the study and the potential risks and benefits known, or that can be reasonably predicted or expected. These risks are described in the consent. Subjects shall have sufficient opportunity to consider participation in the study. The investigator will explain the research study to the potential Subject, discuss their rights as research Subjects, and answer any questions that arise.
- 18.3. Subjects are then invited to sign and date the consent form, indicating their consent for enrollment. The investigator administering the consent will also sign and date the form to indicate the document was sufficiently explained and the Subject signature was witnessed. Only the Investigator or study personnel expressly approved by their ethics committee may administer consent. The Investigator will retain the original copy of the consent form, signed, and dated by the Subject, in the Investigator's study file. A duplicate shall be provided to the Subject, who is now a subject of the trial.
- 18.4. Subjects may withdraw consent to participate at any time without prejudice. Data collected prior to withdrawal will be included in the analyzed data set.

19. Study Budget

- 19.1. A study budget will be provided to the investigator which will include subject compensation. Subjects will receive reasonable compensation for their time and participation in the study.

20. Publication

- 20.1. Individual centers may use their results for publication and presentation, but the Sponsor has the right to review the material prior to submission for publication/presentation. Additionally, the Sponsor has a right to collaborate with study sites on publications and presentations

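### The survey content described in 9.2 does not give the matched baseline and 1-week measurements that the Aim 2 change summary in 13.3.1 needs

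*Combined protocol and SAP*

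**What the plan says.** Section 2.2 gives Aim 2 as "To compare changes in participant streaming behavior and satisfaction with bimodal streaming from Baseline to 1-Week", and 13.3 repeats it almost word for word. Section 13.3.1 sets the analysis: "The change in subject response from the baseline to 1-week survey will be summarized using descriptive statistics for the following questions/domains". The domains are "Frequency of Bluetooth streaming" (13.3.1.1) and satisfaction with bimodal streaming (13.3.1.2).

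Section 9.2 is the only description of survey content.

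- **Baseline (9.2.1):** the subject's "experience with Bluetooth streaming and their satisfaction ratings of their" "current hearing abilities, hearing devices, and Bluetooth streaming set-up". Subjects who took part in pairing also rate its ease of use.
- **1 week (9.2.2):** whether the Bluetooth connection was maintained, how far several aspects of listening improved when streaming with AudioKey, how far overall satisfaction with the hearing devices improved, and how likely continued use is.

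At the baseline visit, pairing and training (10.1.2) are listed before the survey (10.1.3). Participation ends when the 1-week survey is received (10.2.2). Section 11.1.7 admits subjects who have streamed before and also subjects who are only motivated to do so.

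**The concern.** A change in response, even one that is only described, needs the same quantity recorded in the same way at both times. An improvement rating given at 1 week already contains the subject's own comparison with the past. It cannot be subtracted from a baseline satisfaction level or cross-tabulated with it like for like.

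The baseline reference is a second problem. Aim 2 speaks of "satisfaction with bimodal streaming" from baseline onward, whereas the baseline item rates a streaming set-up that may or may not be bimodal. If the survey is completed after pairing and training, a subject asked about the current set-up could rate the old one or the newly paired one. Different subjects could choose differently, and the data would not show it.

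Aim 2 is one of two stated aims. An item left off the 1-week form could not be recovered later under the plan.

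**Working it through.** No arithmetic applies to the main point, because the plan gives no figure to reproduce. The check sets each Aim 2 domain against what 9.2 lists at each time.

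| Aim 2 domain | Baseline (9.2.1) | 1 week (9.2.2) | Matched pair described? |
|---|---|---|---|
| Streaming frequency | Possibly within streaming experience; not named | Not listed. Connection success and likelihood of continued use are not frequency | No |
| Streaming satisfaction | Level rating of the current Bluetooth streaming set-up | Not listed. The only satisfaction item is improvement, and its object is the hearing devices | No |

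**Which set-up is rated at baseline?**

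1. Aim 1 (13.2) is worded "with bimodal streaming when compared to their previous streaming set-up", which favours reading the baseline item as the earlier set-up.
2. Section 9.2.1 says current, not previous.
3. The order in 10.1.2 to 10.1.3, and the pairing ease-of-use item within the same survey, place completion after pairing.
4. The text therefore leaves the reference open.

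**Who can rate it?**

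1. Under 11.1.7, a subject may enter with no streaming experience and hence possibly no set-up to rate. The plan does not say how such a subject enters a change summary.
2. The background text before section 2 says that Android users could already stream directly to both devices, and that iOS users could do so through an intermediary device. Section 10.1.2 allows for the app being on the phone already. Some subjects may therefore be streaming to both ears, or using AudioKey, at enrolment.

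**Effect on the paired n.** The share of subjects with no set-up to rate is not given. Section 7.2 plans 10 to 20 subjects. If k subjects cannot give a baseline rating, the paired satisfaction summary loses k/n of the sample. Each such subject costs 1/10 = 10% at n = 10 and 1/20 = 5% at n = 20. This shows sensitivity only; it does not estimate k.

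**The case against.** The strongest reply is that 9.2 is a short prose summary and does not claim to list every item. The forms are not in the documents. Section 13.3.1 speaks of change between surveys for named questions or domains, which presupposes that both forms carry them. On that view 9.2.2 is merely less complete than 13.3.1. This stands as a limit: the documents show a mismatch between described content and planned analysis, not that the data will be missing. It does not settle the baseline reference or the handling of subjects with nothing to rate, which 13.3.1 does not address.

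The second reply is that the impact is small. Both aims are descriptive, no test or error rate is involved, and Aim 1 is reported from 1-week responses (13.2.1). That is right and keeps the point below a critical grade. But a descriptive change still needs two comparable measurements.

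The third reply is that every subject is a bimodal listener and some could already rate bimodal streaming from experience. That also stands. A reader might infer that bimodal streaming cannot be rated at baseline, or that the comparison is simply a non-bimodal set-up against a bimodal one. The background text does not support either inference.

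**Conclusion.** The point holds as a mismatch between 13.3.1 and 9.2 and should be fixed. As described, neither Aim 2 domain has a like-for-like pair, and the set-up rated at baseline is ambiguous. A reader might go further and conclude that the surveys cannot deliver Aim 2. The documents do not support that, because the forms are unseen and may hold matched items.

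Confidence is high on what 9.2 omits and moderate on the consequence. If the forms follow 9.2, neither planned change can be reported like for like. If they hold matched items, what remains is the wording of the aim, the baseline reference (unless the form states it) and the handling of subjects without a streaming set-up. No amount of lost data can be given. Aim 1 does not depend on paired items.

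**What to change.** Before enrolment, check both forms and make these changes where needed:

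- **Matched items.** Each form carries identically worded and scaled items, apart from naming the set-up being rated, for (a) frequency of Bluetooth streaming, with a never option, and (b) satisfaction with the streaming set-up.
- **Baseline reference.** Have the baseline versions completed before study pairing and training, or word them to refer to the set-up in use at enrolment. The pairing ease-of-use item stays after pairing.
- **Subjects with nothing to rate.** Add a response for no streaming set-up to baseline item (b), and report the paired n.
- **Enrolment set-up.** Record whether it already streamed to both ears or already used AudioKey.
- **Wording.** Bring 2.2, 9.2.1, 9.2.2, 13.3 and 13.3.1.2 into line as *satisfaction with streaming set-up: set-up in use at enrolment vs AudioKey bimodal streaming at 1-week*.

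The improvement ratings can stay as 1-week outcomes for Aim 1. A stated recall window and a shift table are optional.

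The cost is one or two survey items at most, plus the response option, the enrolment record and the text edits. Changed forms may need IRB re-review, since 17.1 covers the protocol and associated materials. The paired satisfaction summary may include fewer subjects.
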